## 3. Statistical Methods

### 3.1 General analysis principles

All primary analyses will involve assessment of all listed primary (effectiveness of delivery options and secondary (reach, effectiveness, adoption, and implementation) outcomes. Intent-to-treat (**ITT**) is a strategy for analyzing data that compares patients in the groups to which they were originally randomly assigned, irrespective of the treatment actually received. The ITT analysis will be the main statistical approach for determining intervention effectiveness. Per-protocol (**PP**) analyses reflect the inclusion in the analysis of patients who strictly adhered to the trial protocol. Based on these general analysis principles, the specific analyses to be conducted are described below.

### 3.2 Dataset assembly, cleaning and creation of new variables

Datasets will be extracted from REDCap, transferred to Stata statistical software, and re-arranged into working analytic files. At first, long format shall be used, but after cleaning and generation of relevant variables, data will be reshaped into a wide format for final analyses. Working analytic datasets will be checked, each variable at a time, for completeness, logical range, and consistency accuracy. Patient adherence data, for both directly observed and digitally confirmed doses, are stored in Everwell 99DOTS adherence database. Dosing reports extracted from the Everwell database containing detailed information on patient adherence, including date and time stamps associated with each dose taken, will be merged with trial data in order to summarize patient treatment adherence and overall treatment completion statistics.

### 3.3 Baseline assessment of patient characteristics

Baseline demographic and clinical characteristics will be assessed for all patients across arms in order to assess achievement of balance across arms by randomization. Characteristics may include but are not limited to: age, sex, prior TB, multidimensional poverty index (**MPI**), ART status, and years on ART.

### 3.4 Primary analysis of primary outcome (intervention effect analysis)

Primary outcome analysis will include the comparing the proportion of those completing at least 11 of 12 doses within 16 weeks from date of treatment initiation for those in the DOT vs. SAT vs. choice arms. This will involve:

1. **Unadjusted intent-to-treat comparisons of effectiveness between arms:** Participants randomized to the choice arm will be treated separately from those randomized to either facilitated DOT or facilitated SAT; the proportion of those in the patient choice arm who choose DOT or SAT will be measured and reported, but the primary outcome will consider all individuals in this arm as randomized to patient choice. The primary outcome using ITT comparisons will be the unadjusted risk ratio and 97.5% two-sided confidence intervals (**CIs**), and Fisher's exact test to determine statistical significance (two-sided alpha of 0.025, including Bonferroni correction).
2. **Simple calculation (using the exact binomial CIs) of the effectiveness of each delivery option, with a target of 80%.** Whether 80% acceptance and completion is achieved will be based on the lower bound of the Bonferroni-corrected 97.5% CI exceeding 0.80 in any of the three arms. We will reject our null hypothesis if the lower bound of the 97.5% CI does not exceed 80%.

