- **Primary outcome** analysis will include: 1) unadjusted intent-to-treat comparisons of effectiveness between arms and 2) simple calculation (using the exact binomial confidence intervals) of the effectiveness of each delivery option, with a target of 80%. In these analyses, participants randomized to the choice arm will be treated separately from those randomized to either facilitated DOT or facilitated SAT; the proportion of those in the patient choice arm who choose DOT or SAT will be measured, but the primary outcome will consider all individuals in this arm as randomized to patient choice. Whether 80% acceptance and completion is achieved will be based on the lower bound of the Bonferroni-corrected 98.3% confidence interval exceeding 0.80 in any of the three arms. The intent-to-treat comparisons will use log-binomial regression to calculate prevalence ratios, and Fisher's exact test to determine statistical significance (two-sided alpha of 0.025, including Bonferroni correction). Participants who decline to initiate 3HP after randomization will be counted as not accepting/completing treatment in the primary (intent-to-treat) analysis and will be followed over time for clinical outcomes.
- **Secondary outcome** analysis will include:
 1. **Reach outcomes:** Analysis will include 1) unadjusted comparisons across arms, 2) per protocol analysis of DOT versus SAT in the choice arm in case of crossover including analysis of outcomes among participants who crossed over against outcomes among those who stayed in their originally selected strategy if a sufficiently large number of patients cross over from DOT to SAT or vice versa and 3) simple calculation of the proportion of patients offered 3HP who accept treatment in each arm. We will also compare this outcome across key demographic variables including age, gender, CD4 stratum, and viral load suppression.
 2. **Effectiveness outcomes:** Analysis of effectiveness outcomes will include the development of TB and the occurrence of adverse events analyzed with Chi-square tests, logistic regression, Kaplan-Meier curves, log-rank tests, and Cox regression methods as appropriate. Any signs or symptoms lasting ≥ 3 days duration (by patient self-report) during the previous month will be recorded and included in our analysis. We will also compare outcomes across key demographic variables including age and gender.

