### 2.3 General comments

This statistical analysis plan covers all effectiveness, implementation, and cost-effectiveness/modelling outcomes. Trial results reporting will follow the CONSORT 2010 statement extension for randomized control trials.

This document summarizes effectiveness outcomes analysis for the primary outcome of the proportion of eligible participants who accept treatment and take at least 11 of 12 doses of RPT/INH within 16 weeks of treatment initiation and secondary outcomes for the implementation and cost-effectiveness of each delivery strategy. These endpoints will be evaluated through review of study documents and study registers for all patients enrolled in the 3HP Options Trial at Mulago ISS Clinic. This Statistical Analysis Plan is written in support of and is predominantly consistent with the full trial protocol version 1.4 (3HP\_Protocol\_Official\_v1.4\_12MAY2022); however, this analysis plan takes precedence.

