## 2.5 Sample Size

We estimated our sample size for the primary outcome (N=1656; 552/arm) based on a minimum clinically important difference of 10% in 3HP completion, comparing patient choice vs. DOT arms. Of note, the Centers for Disease Control and Prevention (**CDC**) TBTC iAdhere study of 3HP delivery strategies chose a 15% non-inferiority margin between DOT and SAT based on cost-effectiveness modeling in the US. We chose 10% to be more conservative because similar modeling studies have not been done in low-income settings, and because ours is not a non-inferiority design. To be maximally conservative, we applied a Bonferroni correction based on two independent comparisons (choice vs. DOT and choice vs. SAT). Assuming a two-sided alpha of 0.025, and 5% loss between consent and allocation, a sample size of 552 participants per arm (N=1656 total) is required to provide power of 0.90 to detect this difference (Table 3). This sample size will also give us power of 0.85 to detect a point estimate of at least 80% effectiveness in the patient choice arm, assuming a true effectiveness of 85%. If the true effectiveness rises to 86%, our power to show effectiveness >80% increases to 0.96. Power was calculated using the PS - Power and Sample Size program.

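### SAP 3.4 tests the 80% target in any of three arms with a 97.5% interval, which corrects for two tests; the protocol's 98.3% corrects for three

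*SAP*

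**What the plan says.** Both documents list two primary hypotheses: that the choice arm will have the highest proportion accepting and completing 3HP, and that this proportion can exceed 80%.

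For the second hypothesis, SAP section 3.4 item 2 uses exact binomial intervals in each arm. Success depends on the "lower bound of the Bonferroni-corrected 97.5% CI exceeding 0.80 in any of the three arms". The Data Analysis text of the protocol, under Primary outcome, gives the same rule at another level: "lower bound of the Bonferroni-corrected 98.3% confidence interval exceeding 0.80 in any of the three arms".

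For the between-arm comparisons the two documents agree on a "two-sided alpha of 0.025, including Bonferroni correction". SAP section 2.5 explains where 0.025 comes from: "we applied a Bonferroni correction based on two independent comparisons (choice vs. DOT and choice vs. SAT)". The protocol's sample size paragraph says the same. Neither document gives any other basis for 0.025 or 97.5%.

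SAP section 2.3 says that where it differs from protocol version 1.4, "this analysis plan takes precedence". The SAP's version history lists three changes. None concerns this confidence level, and the text gives no reason for departing from 98.3%.

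**The concern.** There are two families of tests here. The first is two between-arm comparisons, choice against DOT and choice against SAT. The second is three single-arm tests against 80%, any one of which is enough for a positive claim. The protocol gives each family its own level: 0.025 for the first and 98.3% for the second. The SAP carries the two-test level into the three-test rule and still labels it Bonferroni-corrected.

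Two things are at stake. The chance of wrongly claiming that some delivery strategy exceeds 80% is higher than the stated correction implies. And a primary success threshold has two values on file, so a borderline result could be called either way after the data are seen.

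**Working it through.** **Inputs**

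- 552 participants per arm, from SAP section 2.5.
- Exact binomial intervals and a lower bound above 0.80 in any of three arms, from SAP 3.4 item 2 and the protocol's Data Analysis text.
- Levels of 97.5% (SAP) and 98.3% (protocol).
- Overall two-sided error of 0.05. This is inferred: 0.025 for each of two comparisons gives 2 × 0.025 = 0.05. Neither document states a familywise level for the 80% target.

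**Step 1. Reproduce the two stated levels.** The Bonferroni interval level for k tests is 1 − 0.05/k.

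- k = 2: 1 − 0.05/2 = 0.975, the SAP's figure.
- k = 3: 1 − 0.05/3 = 0.9833, the protocol's figure.

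**Step 2. Nominal error across three arms.** Three 97.5% intervals spend 3 × 0.025 = 0.075 two-sided, against 3 × 0.0167 = 0.05 for three 98.3% intervals. Only the lower bound matters for claiming success, so the error per arm in that direction is half the two-sided value. With independent arms, all truly at 80%:

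- 97.5%: 1 − (1 − 0.0125)³ = 0.0370
- 98.3%: 1 − (1 − 0.00833)³ = 0.0248

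**Step 3. Exact pass marks at n = 552.** The lower bound for x completers is the (1 − level)/2 quantile of a Beta(x, 552 − x + 1) distribution.

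| Completers | Proportion | Lower bound, 97.5% | Lower bound, 98.3% |
|---|---|---|---|
| 462 | 83.7% | 0.7986 | 0.7959 |
| 463 | 83.9% | 0.8005 | 0.7978 |
| 464 | 84.1% | 0.8025 | 0.7998 |
| 465 | 84.2% | 0.8044 | 0.8018 |

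An arm passes from 463 under the SAP and from 465 under the protocol. At 463 and 464 the documents give opposite verdicts.

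**Step 4. Exact error at these pass marks,** with X binomial (552, 0.80).

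- SAP: P(X ≥ 463) = 0.0116 per arm. Across three arms, 1 − (1 − 0.0116)³ = 0.034.
- Protocol: P(X ≥ 465) = 0.0063 per arm. Across three arms, 1 − (1 − 0.0063)³ = 0.019.

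**Step 5. Power per arm at these pass marks.**

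| True proportion | SAP, 97.5% | Protocol, 98.3% |
|---|---|---|
| 85% | 0.789 | 0.716 |
| 86% | 0.931 | 0.894 |

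Both documents state power of 0.85 at a true 85% and 0.96 at a true 86%. With exact intervals neither level reproduces these. An uncorrected exact 95% interval does: the pass mark is 461 and power is 0.850 and 0.957. A 97.5% normal-approximation interval using the variance at the true proportion also comes close, at 0.853 and 0.966.

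**The case against.** The contradiction and the arithmetic are not in dispute. The case on the other side is about weight and about the fix.

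- **The error stays below 5%.** The claim runs in one direction only. Under the SAP's rule the chance of any false claim is at most 3 × 0.0125 = 3.75%. Had the plan set a one-sided 5% for this family, a 96.7% interval would be enough (1 − 2 × 0.05/3 = 0.967), and 97.5% would be stricter than needed. This is correct arithmetic, but neither document adopts a one-sided 5%. The SAP claims a Bonferroni correction, and the only convention that explains both its 0.025 and the protocol's 98.3% is a two-sided 0.05.
- **The zone of disagreement is narrow.** It covers two counts. The chance that a given arm lands there is 0.0116 − 0.0063 = 0.5% at a true 80%, and 0.789 − 0.716 = 7% at a true 85%. The between-arm tests and the point estimates are untouched. This stands as a limit on practical effect.
- **Precedence is not certain.** The clause names protocol version 1.4, and the version of the protocol supplied is not visible. That protocol contains a 28-month TB objective that the SAP's objectives lack, so it may be a later version. This also stands, but the two texts conflict whichever governs.
- **The fix touches more than one number.** The level appears twice in SAP 3.4 item 2. The second sentence also says the null is rejected when the lower bound does not exceed 80%, which reverses the rule. The stated power moves further from the exact value when the level rises. These are separate defects, best corrected in the same revision.

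**Conclusion.** The concern holds. The SAP's rule has three chances of success, and its level corrects for two. The protocol gives the three-test level for the same rule, and no reason is offered for the difference.

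The size is modest: the pass mark is two completers lower per arm, and the chance of at least one false claim is 3.4% instead of 1.9% exactly, or 3.7% instead of 2.5% nominally. These figures assume 552 analysed per arm, independent arms all truly at 80%, and an overall two-sided 0.05 inferred from the two-comparison correction. The false-claim rate stays under 5% in one direction. The reason to act is less the size of the inflation than that a primary hypothesis has two decision thresholds, and the one in the document that claims precedence does not match its own label.

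**What to change.** In SAP section 3.4 item 2, replace 97.5% with 98.3% (1 − 0.05/3) in both sentences where it appears. Keep 97.5% for the between-arm risk ratios in item 1. In the same revision, correct the second sentence so that the null is rejected when the lower bound does exceed 80%.

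No change to data collection or conduct is needed. The pass mark rises from 463 to 465 of 552, and power at a true 85% falls from 0.79 to 0.72. The power statement in SAP section 2.5 and in the protocol's sample size paragraph should be restated for the interval actually used, because 0.85 matches neither level with exact intervals.

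If the sponsor prefers 97.5%, the alternative is to state the error rate intended for the three-arm rule, drop the Bonferroni label for this test and amend the protocol to agree. Either way the choice should be recorded before arm-level outcomes are seen.

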### 2.2 Primary hypotheses:

1. The proportion who accept and complete 3HP will be highest among PLHIV randomized to the informed choice arm.
2. The proportion of PLHIV who accept and complete 3HP can exceed 80% in a high HIV/TB burden setting.

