### Power to detect 10% difference

Effectiveness		Power
DOT	Choice	
70%	80%	0.90
75%	85%	0.94
80%	90%	0.98
85%	95%	0.998

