effectiveness of each delivery option, with a target of >80%, and 3) comparisons of risk ratios and 97.5% two-sided CIs of effectiveness between arms, adjusted for unbalanced characteristics or pre-specified characteristics measured in the baseline survey. We will assess for differences in the ITT and PP analysis populations by comparing baseline characteristics such as age, sex, antiretroviral therapy (**ART**) status, time on ART and prior TB.

3. **Assessing our primary outcome to estimate an as treated estimate that reflects the difference in treatment completion rates in patients** classifying participants based on which delivery strategy they actually received, irrespective of which arm they were allocated to. This will involve 1) allocating choice participants to either DOT or SAT arm, 2) making unadjusted comparisons of risk ratios and 97.5% two-sided CIs of effectiveness between arms, 3) simple calculation (using the exact binomial CIs) of the effectiveness of each delivery option, with a target of 80% and 4) comparisons of risk ratios and 97.5% two-sided CIs of effectiveness between arms, adjusted for unbalanced characteristics or pre-specified characteristics measured in the baseline survey.

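### The rejection sentence for the 80% completion target is reversed, and the stated choice-arm power does not fit the planned exact interval when read as two-sided

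*SAP*

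**What the plan says.** SAP 2.2 gives the second primary hypothesis: "The proportion of PLHIV who accept and complete 3HP can exceed 80% in a high HIV/TB burden setting". SAP 3.4 item 2 tests it with exact binomial intervals, one per arm, and judges success "based on the lower bound of the Bonferroni-corrected 97.5% CI exceeding 0.80 in any of the three arms". The item closes with: "We will reject our null hypothesis if the lower bound of the 97.5% CI does not exceed 80" percent. No null hypothesis is defined anywhere in the SAP.

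Item 1 of the same section, on the between-arm comparison, specifies the "unadjusted risk ratio and 97.5% two-sided confidence intervals". Item 2 gives the level only.

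The protocol (Statistical Considerations, Data Analysis, Primary outcome) has the same any-of-three rule with exact intervals, but at 98.3% and without the closing sentence.

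On power, SAP 2.5 and the protocol's sample-size paragraph both claim "power of 0.85 to detect a point estimate of at least 80% effectiveness in the patient choice arm, assuming a true effectiveness of 85" percent, and 0.96 if the true rate is 86%. SAP 2.5 also explains where its alpha of 0.025 comes from: "we applied a Bonferroni correction based on two independent comparisons (choice vs. DOT and choice vs. SAT"). SAP 2.3 says the SAP prevails over the protocol.

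**The concern.** Three things are unsettled in the decision rule for a primary hypothesis.

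- **Direction.** Under the natural null (completion of 80% or less), the closing sentence rejects exactly when the data fail to support exceeding 80%. It contradicts the sentence before it.
- **Sidedness and power.** Two-sided is the ordinary reading of an exact confidence interval, but the stated power does not fit it. If the interval was meant as a one-sided bound, false passes are more frequent than 5% across three arms. If it was meant as two-sided, the trial is less likely to show the target in the choice arm than the documents say.
- **Level (smaller).** The SAP calls 97.5% Bonferroni-corrected for a rule over three arms, but its 0.025 was derived for two pairwise comparisons. The protocol uses 98.3%, which is 1 − 0.05/3, for the same rule.

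A primary rule with more than one reading leaves room to choose the reading after the results are known.

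**Working it through.** **Direction.** SAP 2.2 looks for a proportion above 80%. The first rule in SAP 3.4 item 2 and the protocol both require the lower bound to exceed 0.80. SAP 3.5 item 2 describes the "effectiveness of each delivery option, with a target of >80" percent. Only the closing sentence of item 2 points the other way. Taken literally with a two-sided 97.5% interval, it would reject at 462 or fewer completers out of 552. The probability of that is 0.988 at a true rate of 80% and 0.211 at 85%.

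**Inputs.** n = 552 per arm, with all randomized participants in the denominator (SAP 2.4, 2.5). Threshold 0.80. Exact binomial (Clopper-Pearson) intervals (SAP 3.4; protocol Data Analysis). True rates 0.85 and 0.86 (SAP 2.5).

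**Method.** For lower-tail area t, the pass mark r is the smallest count whose exact lower bound exceeds 0.80. Equivalently, it is the smallest r with P(X ≥ r | 552, 0.80) ≤ t. Power is P(X ≥ r | 552, p). With independent arms all at 80%, the chance of at least one false pass is 1 − (1 − a)³, where a = P(X ≥ r | 552, 0.80).

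**Reproducing the stated figure.** With t = 0.025, r = 461. Power is 0.850 at 85% and 0.957 at 86%, matching the stated 0.85 and 0.96. A lower tail of 0.025 is a one-sided 97.5% bound or, identically, an uncorrected two-sided 95% interval.

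**All readings:**

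| Reading | Tail t | r | a | Power at 85% / 86% | Any-arm false pass |
|---|---|---|---|---|---|
| One-sided 97.5% (= two-sided 95%) | 0.025 | 461 | 0.0203 | 0.850 / 0.957 | 1 − 0.9797³ = 6.0% |
| One-sided 98.3% | 0.0167 | 462 | 0.0154 | 0.821 / 0.945 | 4.6% |
| Two-sided 97.5% | 0.0125 | 463 | 0.0116 | 0.789 / 0.931 | 3.4% |
| Two-sided 98.3% | 0.0083 | 465 | 0.0063 | 0.716 / 0.894 | 1.9% |

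The literal wording, power to detect a point estimate of at least 80%, does not explain the figure either: P(X ≥ 442 | 552, 0.85) is about 0.999. A smaller n does not help: at 497 per arm (552 less 10%), a tail of 0.025 gives 0.810 and 0.936.

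**Any-of-three chance of success.** The stated power concerns one arm, but the rule passes if any arm passes. With choice at 85% (single-arm power q) and each other arm passing with probability s, the chance is 1 − (1 − q)(1 − s)²:

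| Other two arms | Two-sided 97.5% | Two-sided 98.3% |
|---|---|---|
| 75% | 0.789 | 0.716 |
| 80% | 0.794 | 0.719 |
| 85% | 0.991 | 0.977 |

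The 75% row follows the DOT 75% / choice 85% line of the SAP table "Power to detect 10% difference"; SAT at 75% is an assumption. The chance reaches 0.85 once both other arms are at about 82.1% (97.5%) or 83.2% (98.3%).

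**Level alone.** Two-sided 97.5% and 98.3% disagree only at 463 or 464 completers in an arm. That has probability 0.5% at a true 80% and at most about 9%, near 84%.

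**The case against.** The strongest reply is that this is a slip with no practical ambiguity. The correct rule stands in the sentence immediately before, and nobody would declare success because the target was missed. Two-sided is the conventional meaning of an exact interval, and item 1 uses that term. On that reading the false-pass chance is 3.4%, and three tails of 0.0125 sum to 3.75%, so error stays below 5% even without independence. The power sentence is ancillary: the sample size was set by choice versus DOT, and the text does not say that 0.85 refers to the corrected bound. A normal approximation using only the variance under the alternative, at two-sided 97.5%, gives 0.853 and 0.966, close to the stated pair.

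Much of this is fair. The intended direction can be inferred, the level difference is small, and the sample size is unaffected. What remains is that the governing document contains a sentence contrary to its own rule, and that the published power does not describe the planned test. The approximation appears in neither document as the analysis, and it rounds to 0.97 rather than 0.96 at a true 86%. If the stated figure is simply uncorrected single-arm power, it still needs correcting, because the decision uses a corrected bound.

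**Conclusion.** The concern holds. The closing sentence of SAP 3.4 item 2 is reversed and the null is undefined. With the planned exact interval read as two-sided, choice-arm power at a true 85% is 0.79 at the SAP's level or 0.72 at the protocol's, against a stated 0.85. At a true 86% it is 0.93 or 0.89, against 0.96. The stated power requires a 0.025 lower tail, which allows a 6.0% chance of a false pass somewhere among the three arms. None of the four readings gives both the stated power and a false-pass chance below 5%. The two-sided reading is sound on error control, so there the cost is an overstated power, not an invalid test.

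These figures assume exactly 552 randomized per arm and, for the any-arm chances, independent arms; the false-pass figures take all three at exactly 80%. The power figures are for the choice arm alone; the chance that some arm passes is higher if DOT or SAT also does well. This should be fixed before analysis, but it does not threaten the design.

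**What to change.** In SAP 3.4 item 2:

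1. Define the null for each arm: true acceptance and completion is 80% or less.
2. Replace the closing sentence with: *The null is rejected for an arm if the lower limit of its two-sided exact confidence interval, at the level given above, exceeds 80%.* Keep the preceding any-of-three sentence, which says how the arm results combine.
3. Use one level in both documents. Either take 98.3% two-sided, as in the protocol, or keep 97.5% two-sided and give the reason it is adequate for three arms (3 × 0.0125 = 0.0375, below 0.05).

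In SAP 2.5 and the protocol's sample-size paragraph, restate the choice-arm power at the chosen level: 0.72 and 0.89 at 98.3%, or 0.79 and 0.93 at 97.5%. Say that it is a single-arm figure, and replace the reference to a point estimate with the lower-bound criterion.

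The cost is wording and a less favourable stated power. Choosing 98.3% raises the pass mark by two completers per arm, from 463 to 465. Sample size and data collection stay as they are.
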